### **16.5 Analysis of adverse events**

All adverse events (AE; any undesirable experience occurring to a participant during the trial, whether or not considered related to the study medication) reported by the subject or observed by the investigators will be recorded at each visit. Standard procedures for reporting of (serious) adverse events will be used. (Serious) adverse events will be summarized as frequencies and percentages by treatment group. For recurrent events and to account for variable follow-up times event rates will be reported with rate ratios comparing Simvastatin with add-on placebo control and 95% confidence intervals. We will use Poisson regression models with adjustment for over dispersion (or negative binomial regression models) with offset for follow-up time and possibly a mixture component to account for zero-inflation. For events of particular interest Kaplan-Meier curves stratified by treatment group will be computed and compared by log-rank tests.

### **16.6 Interim analyses and endpoints for premature study termination**

As the analyses will be adjusted for baseline scores the actual power is likely to be higher than 80 %. To confirm this in an interim analysis, a blinded sample size review will be carried out once 50 % of the patients have reached week 12. Based on blinded estimates of the mean square error and the dropout rate the required sample size will be recalculated and the sample size will be adjusted up to a maximum total sample size of 240 patients, if necessary.

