### 16.2 Sample size estimation

So far, there are three small pilot RCTs in depressed patients (sample sizes ranging from  $n = 48$  to  $n = 68$ ) that have all found statistically significant beneficial effects of add-on statins vs. placebo with large, clinically relevant effect sizes. A meta-analysis [2] of these trials has found a standardized mean difference between add-on statins and add-on placebo of  $-0.73$  (95 % confidence interval  $-1.04$  to  $-0.42$ ,  $p < 0.001$ ). However, it is well-known that initial studies tend to overestimate the true effect size [78]. Therefore, we conservatively assume a standardized treatment difference (also known as Cohen's  $d$ ) of  $0.5$ , which is supported by the findings of all pilot RCTs [36, 79, 80]. Given a standard deviation of 6-8 points on the MADRS, as commonly observed in RCTs in this population [81-83], a standardized effect size of  $0.5$  translates into a mean difference of 3-4 points, which is considered clinically relevant because it is about twice as large as the minimal clinically important difference of 1.6 to 1.9 points that has been reported [84]. Thus, a sample size of 64 patients per group gives a power of 80% for a comparison of the mean changes in MADRS score from baseline to week 12 between the two treatment groups using a two-sample t-test at the usual two-sided level of 5%. As the analyses will be adjusted for baseline scores the actual power is likely to be higher; this will be confirmed in a blinded sample size review once 50% of the patients have reached week 12 [85]. Accounting for about 20% dropout, we aim to recruit 80 patients per group (i.e. 160 patients in total). Based on sex-specific prevalence rates and recruitment in our earlier studies [86, 87], we expect that about two thirds of the sample will be women. This will allow gender-specific analyses.

**Figure 4:** Study flow chart according to CONSORT. We assume that we need to screen  $N = 1125$  patients aged 18 - 65 with major depression according to Diagnostic and Statistical Manual of Mental Disorders (DSM) 5 and obesity (body mass index  $\geq 30$ ) for eligibility at 8 recruiting centers to randomize  $n = 160$  participants. The sample size and assumed dropout rate (20%) is conservatively based on three earlier pilot RCTs of add-on statin to SSRI treatment in depressed patients [1-3].

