### 16.4 Analysis of primary and secondary endpoints

The primary analysis will compare MADRS changes from baseline to week 12 between the Simvastatin and placebo group by Gaussian linear models for repeated measures (so-called MMRM) with intervention, center, time (week 1, 2, 4, 8, and 12), and intervention-by-time interaction as factors, and baseline MADRS score as covariate. The error terms are assumed to follow a multivariate normal distribution with unstructured covariance. Least squares mean changes from baseline will be reported for both groups with 95% confidence interval (CI) as well as the difference between the least squares treatment group means with 95% CI and p-value testing the null hypothesis of no treatment effect. Although the model described above is robust to a certain extent to missing data, sensitivity analyses will be performed as supporting analyses including multiple imputation and last-observation-carried-forward (LOCF). The latter will also facilitate comparison with previous trials.

The analyses of all secondary endpoints and safety parameters will have an exploratory character and will therefore not be adjusted for multiple testing. The secondary efficacy endpoints MADRS-response and MADRS-remission, and MADRS-MCID within 12 weeks will be analyzed by logistic regression models with intervention and center as factors and baseline MADRS as covariate. The treatment effects will be reported as odds ratios with 95% CI and p-values testing the null hypotheses of no treatment effect. The analyses of continuous secondary efficacy endpoint as well as SOFAS, and EQ-5D-3L will follow the same lines as the primary outcome.

We will repeat the analyses in the per-protocol sample.

All details of the statistical analyses including definitions of the analyses populations will be specified in the statistical analysis plan, which will be finalized before database lock and unblinding. All statistical analyses will be carried out using SAS software (SAS Institute Inc., Cary, NC, USA) or the R package.

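### Does the blinded sample size review in section 16.6 need a MADRS difference in points fixed in the plan before it can be run?

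*Combined protocol and SAP*

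**What the plan says.** Section 16.2 sets the planning effect in standardised units: "we conservatively assume a standardized treatment difference" (Cohen's d) of 0.5. It then states "Given a standard deviation of 6-8 points on the MADRS", so that 0.5 "translates into a mean difference of 3-4 points". On that basis "a sample size of 64 patients per group gives a power of 80" percent, "using a two-sample t-test at the usual two-sided level of 5" percent. Allowing for about 20% dropout, this becomes 80 per group, 160 in total. The section adds that baseline adjustment probably makes true power higher, and cites a methods paper on blinded recalculation with baseline-adjusted analysis.

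Section 16.6 places the review at the point where half the patients have reached week 12. Its first stated purpose is to confirm that power exceeds 80%. On the mechanism it says "Based on blinded estimates of the mean square error and the dropout rate the required sample size will be recalculated", and that "the sample size will be adjusted up to a maximum total sample size of 240 patients" if necessary. It names no difference in MADRS points.

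Section 16.4 says that analysis details "will be specified in the statistical analysis plan, which will be finalized before database lock and unblinding".

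**The concern.** A required sample size depends on the ratio of a difference to an SD. The review supplies a new SD, so the difference must come from the plan, and the plan gives either a standardised value or a range in points.

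- If 0.5 is held fixed relative to the residual SD, the required number is 64 per group whatever the MSE turns out to be. Only dropout can then move N, and the MSE input does nothing.
- If 0.5 is tied to the unadjusted SD, the adjusted MSE can show a gain in power, but a variance larger than planned still cannot raise N.
- If points are used, N scales with the inverse square of the difference, so 3 and 4 points differ by a factor of (4/3)² = 1.78.

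The same blinded data could therefore pass or fail the 80% check depending on which end of 3-4 points is used. Section 16.4 ties the SAP to database lock, which comes after this review, so the protocol does not show that the difference will be settled before the pooled SD is known. At stake are the final N, anywhere from 160 to 240, and the meaning of the power statement.

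**Working it through.** **Inputs.** From section 16.2: two-sided 5%, 80% power, d = 0.5, SD 6-8, 3-4 points, 20% dropout, 64 evaluable and 80 recruited per group. From section 16.6: cap of 240. Assumptions: a residual SD of 7 (midpoint of 6-8), a baseline correlation ρ where stated, and 160 as the minimum N.

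**Formulas.** Power of a two-sample t-test with n per group uses the noncentral t with 2n − 2 degrees of freedom and noncentrality δ/(σ√(2/n)). Total recruited = 2 × ceil(n/(1 − dropout)). Residual SD after baseline adjustment = σ√(1 − ρ²).

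**The plan's own figure.** d = 0.5 and n = 64 give 80.1%. Then 64/0.8 = 80 per group, 160 in total. The plan reproduces.

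**Required total N before applying the minimum or the cap (20% dropout):**

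| Residual SD | 3 points | 3.5 points | 4 points |
|---|---|---|---|
| 6 | 160 | 120 | 94 |
| 7 | 218 | 160 | 126 |
| 8 | 284 | 208 | 160 |

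**Power at residual SD 7:**

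| Evaluable per group | 3 points | 3.5 points | 4 points |
|---|---|---|---|
| 64 | 67% | 80% | 89% |
| 80 | 77% | 88% | 95% |

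**If 6-8 is the unadjusted SD.** Section 16.2 gives 6-8 as an SD on the MADRS and does not call it baseline-adjusted. With ρ = 0.5, SD 7 becomes 7 × √0.75 = 6.06.
- 3 points: n = 66 per group, total 2 × ceil(66/0.8) = 166, power at 64 per group 79%.
- 4 points: below the 160 minimum, power 96%.
- With ρ = 0.6 the residual SD is 5.6, and both ends pass 80% (85% and 98%).
- At the top of the range, SD 8 with ρ = 0.5 gives 6.93. There 3 points needs 214 and 4 points stays at 160, so the cap is not reached.

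**If d = 0.5 is kept.**
- On the residual SD, only dropout acts: 25% gives 2 × ceil(64/0.75) = 172, and 30% gives 2 × ceil(64/0.70) = 184.
- On the unadjusted SD, the effective d is 0.5/√(1 − ρ²). For ρ = 0.3, 0.5 and 0.6 this is 0.524, 0.577 and 0.625, and power at 64 per group is 84%, 90% and 94%.

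**The case for a change.** The strongest case for changing the plan is that none of the available readings makes the review fully defined. Holding d fixed removes the effect of the MSE or lets it act only downward. Using points requires a choice that the protocol does not make. The deferral to the SAP does not guarantee that the choice precedes the pooled SD, and a method citation does not select 3 or 4 points for this trial. All of that stands as a description of the text.

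Its weight is limited in four ways.

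1. The contrast of 67% with 89% takes 7 as a residual SD, which gives baseline adjustment no credit, and it assumes 20% of patients contribute nothing at week 12. The primary repeated-measures model keeps partial data, and section 11.1 requires follow-up to week 12 after premature termination, so real power may lie between the 128- and 160-patient figures.
2. The largest figures (284 patients needed, or 73% power at the cap of 240) combine 3 points with SD 8. Section 16.2 pairs 3 with 6 and 4 with 8, each giving d = 0.5.
3. On the reading with d tied to the unadjusted SD, the review can still do its first stated job of confirming power, and dropout can still raise N. What is undefined is how far an unexpectedly large variance would raise N.
4. Section 16.4 sets a latest date for the SAP. It does not exclude an earlier one.

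Naming one difference would not complete the rule either. A blinded pooled variance contains the treatment difference: with 3.5 points and a within-group SD of 7, the pooled SD is √(49 + 3.5²/4) = 7.2, and the total becomes 2 × ceil(68/0.8) = 170 rather than 160. Such operating details are ordinarily settled by the statistician carrying out the review.

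**Conclusion.** The text does leave the difference in points open, and the arithmetic behind the concern is right. It is nonetheless a gap that the analyst has to fill in order to act: an MSE yields no sample size until a difference is entered, and the plan's range of 3-4 points brackets the sensible values. The midpoint pair, 3.5 points with SD 7, returns exactly the planned 64 per group.

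An unfortunate choice would cost recruitment effort or power, and the exposure is bounded. N cannot exceed 240. At residual SD 6 no value in the range needs more than 160. With the midpoint SD 7 unadjusted and ρ = 0.5, the two ends of the range differ by 6 patients (166 against 160). The spread is wider if the residual SD itself reaches 7 (218 against 160). These sizes rest on assumed values for the residual SD, the baseline correlation and the 160 minimum.

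Because the review uses blinded estimates, no bias in the treatment comparison and no type I error problem follows from the open choice. The planned 80% power at d = 0.5 is correctly computed, and the primary analysis is valid at whatever N results. The trial's conclusions would be sound under the plan as written, so no change is called for.

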## **17. Reporting**

### **17.1 Statistical report**

The statistical analysis and the biometrical report will be provided by the biostatistician [name]. [name], Universitätsklinikum Göttingen, in cooperation with the Sponsor representative / Principal investigator. All data in this report is confidential.

### **17.2 Final report**

The composition of a final integrated report will be conducted in accordance with ICH E3: Structure and Contents of Clinical Study Reports. After termination of the biometrical analysis, the biostatistician will compose an integrated report. This report contains a clinical record, a statistical record, single value tables and conclusions. It will be signed by the principal investigator and the biostatistician.

### **17.3 Publication (policy)**

The study results will be published irrespective of the study outcome.

## **18. Ethical, legal and regulatory aspects**

### **18.1 ICH-GCP-guidelines**

This trial will be conducted in accordance with the current ICH-GCP-guidelines. Good Clinical Practice (GCP) is an international ethical and scientific quality standard for designing, conducting, recording and reporting trials that involve the participation of human subjects. Compliance with this standard provides public assurance that the rights, safety and well-being of trial subjects are protected, consistent with the principles that have their origin in the Declaration of Helsinki, and that the clinical trial data are credible.

### **18.2 Legal requirements of the study**

#### *18.2.1 Approval of Ethics Committee*

Study protocol, patient information (Information zur Studie) and consent form (Einwilligungserklärung) will be presented to the relevant Ethics Committees for survey. The study will only start after ethics approval has been granted. The Ethics Committee will immediately be informed (by the Sponsor/Sponsor representative) of all changes to the protocol (according to GCP-V § 10) and of all events that could affect a patient's safety. The Ethics Committee will also be informed of all suspected SUSARs and of regular or premature termination of the study. We will register our study in the ClinicalTrials.gov database and German Clinical Trials Register (DRKS) before we enroll any patients.

#### *18.2.2 Approval of competent authority*

The trial will be submitted to the relevant federal authorities (BfArM) for approval. The trial will only start after approval has been granted.

#### *18.2.3 Notification to regional authorities*

The trial will be submitted to the relevant state authorities by the Sponsor representative / Principal investigator before we enroll any patients. The Sponsor/Sponsor representative and all investigators will be reported by full name.

#### *18.2.4 Patient information and informed consent*

##### **Patient Information**

Before enrolment every patient will receive full oral and written information about the nature, purpose, expected advantages and possible risks of the trial.

##### **Consent to participation in the trial:**

The patient will agree to participation in the trial by signing the informed consent form. Patients must be given an opportunity to enquire about details of the study. After a sufficient period of time for the individual's consideration and decision, comprehension and consent shall be documented on the consent form by the dated signature of the patient and the investigator/subinvestigator. Design and language will be adjusted to the study site's needs. The final versions of patient information and consent will be presented to the Ethics Committee. Both the patient information and the patient consent form are prepared in duplicate. One of each form for the investigator, a duplicate will be handed to the patient.

#### ***18.2.6 Data Privacy and confidentiality***

The participants' data will be saved in a pseudonymous form, which will neither contain initials nor full date of birth. All regulative requirements applying to data protection will be met. Re-identification of a participant subject's name is possible from the patient identification log, which is kept in a locked research office at the study site where access is only possible by the investigator or persons authorized by the investigator.

Patients will be informed that their disease-related data will be saved for scientific purpose (publication, etc.) using a pseudonym. Consenting patients have got the right to be informed about the data recorded. Patients will also be informed that their pseudonymized data will be forwarded to the federal authorities (BfArM) and to the Ethics Committee responsible, in accordance with legal notification obligation for drug safety. Patients, who disagree with this process of data transfer, are not allowed to participate in this study.

Blood samples will be pseudonymized and sent to the local laboratories for analysis. They will be destroyed after analysis (laboratory safety, laboratory assessment lipid) or will be stored for a maximum of 10 years (laboratory assessment immunometabolism / mitochondrial function). The pseudonymized data will be transferred to the study site.

#### **18.3 Archiving of data / Access to records**

Essential documents, as listed below, must be retained by the investigator for as long as needed to comply with national and international regulations. The investigator agrees to adhere to the document retention procedures by signing the protocol. Essential documents include:

- IRB/IEC approvals for the study protocol and all amendments
- All source documents and laboratory records
- Patient identification log
- CRF copies (paper copies or electronic copies on a CD-ROM)
- Signed patient informed consent forms
- Any other pertinent study document.

Originals of all study-related report (incl. original data of study patient - medical records) forms will be stored in each study site for at least 10 years after completion of the trial.

A list allowing patient identification will be kept for 10 years.

#### **18.4 Financing**

The study is funded by the *Bundesministerium für Forschung und Bildung* (BMBF; Federal Ministry of Education and Research) within the call „Klinische Studien mit besonderer Relevanz für die Patientenversorgung“

## **20. Appendices**

### **20.1 Stellungnahme zur Geschlechterverteilung**

Based on sex-specific prevalence rates and recruitment in our earlier studies [86, 87], we expect that about two thirds of the sample will be women. This will allow gender-specific analyses.

### **20.2 Stellungnahme zur Weiterbehandlung nach Studienende**

After completing all the protocol treatment and visits, patients will continue with regular visits according to usual practice. In case of response or remission, Escitalopram will be continued while the study medication Simvastatin (IMP) will be discontinued in any event. In case of non-response or non-remission, Escitalopram will be definitely discontinued. The investigator will ensure a gradual dose reduction of Escitalopram over at least one or two weeks because of potential symptoms associated with abrupt discontinuation of Escitalopram. Patients with non-response or non-remission will be offered at least one additional clinical appointment at the psychiatric outpatient clinic of the study center after termination of the individual study participation for the gradual discontinuation of Escitalopram.

In the case of premature termination, the reason for withdrawal must be entered on the appropriate case report form (eCRF) page and the patient must be followed for safety and efficacy until the end of the study (week 12).

### **20.3 Zusammenfassende Nutzen-Risiko-Abwägung**

See 10. Risk-benefit-assessment

### **20.4 Ergänzende Informationen zum Prüfpräparat**

See 4.2 Data on IMP-Application
